3.1 Research Design Outline

The study aims to perform a comparative study on chronic ankle instability with Kinesio phobia in Saveetha college of physiotherapy and Saveetha college of allied health sciences.

Formerly titled "Effectiveness of Three Typical Yoga poses and Conventional Physiotherapy for Kinesio phobia Among Football Players with Chronic Ankle Instability: A Comparative Study" involves amateur football players with Kinesio phobia by using the Tampa scale for Kinesio phobia and Cumberland ankle instability tool for Chronic ankle instability. The outcome is the total fear of movement, and fear of re-injury, severity of functional ankle instability. Total scores of 68 for Kinesio phobia, 30 for chronic ankle instability. Higher score means a better outcome.

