3.5 Assessment & Outcomes Measures

3.5.1 Primary outcomes

Tampa scale:

The Tampa scale will initially be used to distinguish between non-excessive fear and phobia in patients with chronic musculoskeletal pain, i.e., the fear of movement. In its original form, the TSK will be a 17-item assessment checklist. It will use a 4-point Likert scale (Strongly Disagree-Disagree-Agree-Strongly Agree) with statements that will later be linked to the model of fear-avoidance, fear of work-related activities, fear of movement, and fear of re-injury.

Cumberland ankle instability tool (CAIT):

The Cumberland Ankle Instability Tool (CAIT) will be a 9-item, 30-point scale that will measure the severity of functional ankle instability. Using a numeric value, the

Cumberland Ankle Instability Tool (CAIT) will have the ability to discriminate between stable and unstable ankles.

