4.1 Primary Outcomes

The primary analyses will compare experimental vs control group guidelines on their mean and standard deviation: (i)Tampa scale, (ii) Cumberland ankle instability tool (CAIT).

Comparison will be tested by using the Paired t test to find the significant difference within the intervention effects and between the two groups (Experimental control group and Experimental Group) using independent t-test. P values <0.05 has been considered statistically significant.

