4.2 Secondary Outcomes

The primary analyses will compare experimental vs control group guidelines on their mean and standard deviation: (i) Y-balance test (ii) Pain anxiety symptom scale.

Comparison will be tested by using the Paired t test to find the significant difference within the intervention effects and between the two groups (Experimental control group and Experimental Group) using independent t-test. P values <0.05 has been considered statistically significant.

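### Section 4.1 tests two unranked primary outcomes (Tampa and CAIT) between groups at p<0.05 each, and gives no success rule, order or adjustment

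*Combined protocol and SAP*

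**What the plan says.** - Two instruments, the Tampa scale and the CAIT, stand together under the plural heading "3.5.1 Primary outcomes". Neither is named as the main or first one.
- Section 4.1 of the SAP repeats the pair: "The primary analyses will compare experimental vs control group guidelines on their mean and standard deviation: (i)Tampa scale, (ii) Cumberland ankle instability tool (CAIT". This sentence makes the comparison of experimental with control the primary analysis.
- The next sentence adds a within-group test ("Comparison will be tested by using the Paired t test to find the significant difference within the intervention effects") and the between-group test ("between the two groups (Experimental control group and Experimental Group) using independent t-test"). One threshold covers everything: "P values <0.05 has been considered statistically significant".
- Section 3.1 lists the constructs side by side without ranking them: "The outcome is the total fear of movement, and fear of re-injury, severity of functional ankle instability".
- Section 4.3 fills the score of a player who misses an assessment with the mean of that player's own group.

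The supplied text has no success rule for the two primaries, no testing order, no division of the 0.05 and no multiplicity adjustment. It also gives no sample size, power, sidedness or correlation between the scales.

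**The concern.** Suppose one scale gives p<0.05 and the other does not. Section 4.1 cannot say whether the trial met its primary aim. Three readings fit the text: either scale suffices, both are needed, or each is a claim of its own. They carry different error rates, and a reader of the results could not tell which one was in force. The choice could also be made after the p-values are known. If it then fell on whichever scale had succeeded, the stated 0.05 would understate the chance of a false primary claim.

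**Working it through.** The plan states no joint error rate, so there is no figure of its own to reproduce.

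**Inputs from the documents.** Two primary outcomes (3.5.1, 4.1), one independent t-test for each, and 0.05 per test (4.1).

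**Assumptions.** Two-sided tests, complete data, test statistics bivariate normal with correlation r, and r from 0 to 0.9. Only the two between-group tests are counted. The paired tests are left out because the first sentence of 4.1 makes the group comparison primary.

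**Step 1. Error rate under each reading, both nulls true.**

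- Either scale suffices: 1 − P(|Z1|<1.960, |Z2|<1.960). At r = 0 this is 1 − 0.95² = 0.0975.
- Both scales required: 0.05 + 0.05 − P(either). At r = 0 this is 0.10 − 0.0975 = 0.0025.
- Holm: a false claim needs the smaller p-value below 0.025, so 1 − P(|Z1|<2.241, |Z2|<2.241). At r = 0 this is 1 − 0.975² = 0.0494.

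| r | Either suffices | Both required | Holm |
|---|---|---|---|
| 0 | 9.75% | 0.25% | 4.9% |
| 0.3 | 9.5% | 0.5% | 4.8% |
| 0.5 | 9.1% | 0.9% | 4.6% |
| 0.7 | 8.3% | 1.7% | 4.3% |
| 0.9 | 7.0% | 3.0% | 3.6% |

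With two-sided tests a negative correlation gives the same values. Simulated t-tests with 10, 15 and 30 per group (assumed sizes) gave 9.7% to 9.8% at r = 0 and 7.1% at 0.9.

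If one scale is truly affected, only one true null remains. The chance of a false claim is then at most 5% under any of the readings. Read as two separate claims, each scale keeps 5%.

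**Step 2. Power cost of Holm.** Assume 80% power per scale at two-sided 0.05, that is, a mean test statistic of 1.960 + 0.842 = 2.802.

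| r | Per scale, Holm, both effects real | At least one claim, unadjusted | At least one claim, Holm | Both p<0.05 |
|---|---|---|---|---|
| 0 | 77% | 96% | 92% | 64% |
| 0.5 | 76% | 91% | 85% | 69% |
| 0.7 | 76% | 89% | 82% | 71% |

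If only one effect is real, Holm leaves about 71% on that scale.

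**Step 3. Effect of section 4.3.** Let a fraction m of scores in each group be replaced by the group mean. The sum of squares does not change, but the counted sample size rises. In large samples the t-statistic is multiplied by 1/(1 − m), so the effective cut-off shrinks by (1 − m). With m = 0.10 (assumed; the same in both groups and on both scales):

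- One test: 1.960 × 0.9 = 1.764, and P(|Z|>1.764) = 7.8%.
- Either scale at r = 0: 1 − (1 − 0.0777)² = 14.9%.
- Holm at r = 0: 2.241 × 0.9 = 2.017, P(|Z|>2.017) = 4.37%, and 1 − (1 − 0.0437)² = 8.5%. Simulated t-tests with 20 and 30 per group gave 8.6%.

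**The case against.** The strongest reply is that the plan never says one significant scale establishes success. A reader might infer from 4.1 that it does, and so that this trial's primary error rate is 9.75%. The documents do not support that. The scales measure different things, fear of movement and functional ankle instability, and section 3.1 lists them separately. Two separate claims at 0.05 each is a natural reading, and on it nothing is inflated. This part of the objection stands: the inflation is conditional, and the defect is the missing rule.

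Three further limits also stand.

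- **Sidedness is not stated.** With one-sided tests at 0.05 the sign of the correlation matters: 6.8% at +0.9, 9.75% at 0 and 10.0% at −0.9. So 9.75% is the maximum only for two-sided tests with complete data.
- **The 7.0% lower end is a product of stopping at 0.9.** As the correlation approaches 1, the error approaches 5%.
- **The power figures describe an assumed design.** The documents give no power or sample size, so they show only the order of the cost.

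None of this supplies the rule. The (i)/(ii) labels in 4.1 are list markers, and nothing describes them as a testing order.

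**Conclusion.** The concern holds in a limited form. The plan has two unranked primary outcomes at p<0.05 each, and nothing says what result counts as primary success. That absence is certain for the supplied text; the size is conditional. If either scale alone may be claimed, the tests are two-sided, the data are complete and both nulls are true, the false-claim rate is 7.0% to 9.75% for assumed correlations from 0.9 to 0. Under the other two readings there is no inflation beyond 5% for the claim made.

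A reader might also infer that an adjustment in 4.1 is enough to hold the error at 0.05. It is not if 4.3 is followed as written: at an assumed 10% missing, each test runs at about 7.8%, and Holm at about 8.5% to 8.6% when the correlation is 0.

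**What to change.** In 4.1, before any outcome data are analysed:

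1. State that the two between-group tests are the primary tests and that the within-group paired tests are descriptive.
2. State that Holm applies to the two between-group tests: the smaller p-value must be below 0.025, and then the other below 0.05. Holm needs no ranking of the scales.
3. State that the tests are two-sided, if that is meant.
4. State that the primary tests do not count group-mean imputed values as observed scores, and bring 4.3 into line. Without this, no rule in 4.1 holds the error at 0.05 when assessments are missed.

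A pre-set order of the two scales, or a rule that both must reach p<0.05, is an acceptable alternative. If the sponsor intends two separate claims, 4.1 should say so and say that no joint error rate is controlled.

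**Cost.** The change is SAP wording, in 4.1 and 4.3. On the assumed 80% per scale:

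- Holm costs about 2 to 4 points per scale when both effects are real, and about 9 points when only one is.
- A fixed order keeps 80% on the first scale and gives 64% to 71% on the second. A result on the second scale alone could not be confirmatory.
- Requiring both gives 64% to 71%.

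Editorial only: section 4.2 opens its list of secondary outcomes by calling the analyses primary ("The primary analyses will compare experimental vs control group guidelines on their mean and standard deviation: (i) Y-balance test (ii) Pain anxiety symptom scale"); the word should be secondary.

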3.3 Recruitment

All amateur football players with Kinesio phobia along Chronic ankle instability attending Saveetha Institute of Medical and Technical sciences will be enrolled in the comparative study. The participation information and consent sheet will be distributed to amateur players which details including inclusion and exclusion criteria. Amateur players who agree to the investigation will be invited to undergo baseline assessments Tampa scale, Pain anxiety symptom scale, Y-balance test, Cumberland ankle instability tool (CAIT). All amateur players will have to return a signed consent form to the site principal investigator.

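### Sections 4.1 and 4.2 plan group means, SDs and a P<0.05 criterion, but do not make the between-group difference with its confidence interval the result

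*Combined protocol and SAP*

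**What the plan says.** Section 4.1 introduces the primary outcomes with "The primary analyses will compare experimental vs control group guidelines on their mean and standard deviation", for the Tampa scale and the CAIT. Section 4.2 uses the same sentence, "The primary analyses will compare experimental vs control group guidelines on their mean and standard deviation: (i) Y-balance test (ii) Pain anxiety symptom scale", for the secondary outcomes.

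In both sections the within-group analysis is a paired t-test ("Comparison will be tested by using the Paired t test to find the significant difference within the intervention effects"). The between-group analysis is a t-test "between the two groups (Experimental control group and Experimental Group) using independent t-test". Both end with the same criterion, "P values <0.05 has been considered statistically significant", and neither says whether the test is one- or two-sided.

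The opening paragraph of section 4 adds only that non-normal data are shown as median and interquartile range. Section 4.3 replaces missing assessments with the mean of the player's allocation group. Section 3.3 says that all eligible players "will be enrolled in the comparative study" and gives no target number.

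**The concern.** A comparative study is answered by the difference between the groups and the uncertainty around it. Here the difference is tested, but neither its estimate nor its interval is a planned result.

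That gap matters more than usual because nothing else in the supplied text helps to interpret the P value. There is no sample size, power, detectable difference or outcome SD, so the study's size will be whatever attendance yields. P≥0.05 could then reflect a true absence of benefit or too few players. P<0.05 would carry no statement of how large or small the benefit may be.

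**Working it through.** **Inputs.** The only numerical input from the plan is the 0.05 level (4.1, 4.2), taken here as two-sided. The plan gives no sample size, power or interval, so there is no figure of its own to reproduce. Group sizes, equal allocation and equal SDs are assumptions in steps 1 to 3. Differences are in SD units.

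**1. Width of the missing interval.** Half-width = t(0.975, 2n−2) × √(2/n). At n = 10 per group: 2.101 × 0.447 = 0.94 SD.

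**2. Chance of P≥0.05 with a true benefit of 0.5 SD.** Power comes from the noncentral t with 2n−2 degrees of freedom and noncentrality 0.5 × √(n/2).

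| n per group | 95% half-width (SD) | Power at 0.5 SD | P≥0.05 |
|---|---|---|---|
| 15 | 0.75 | 26% | 74% |
| 20 | 0.64 | 34% | 66% |
| 30 | 0.52 | 48% | 52% |
| 50 | 0.40 | 70% | 30% |

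On the Tampa scale, with an assumed SD of 5 to 8 points, the half-width at 20 per group is 0.64 × 5 = 3.2 to 0.64 × 8 = 5.1 points.

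**3. Same P value, different meaning.** For P = 0.40 the observed difference is t(0.80, 2n−2) × √(2/n).

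- n = 10 per group: 0.862 × 0.447 = 0.39 SD; 95% interval −0.55 to 1.33 SD.
- n = 200 per group: 0.843 × 0.100 = 0.08 SD; 95% interval −0.11 to 0.28 SD.

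The first leaves a large benefit open and the second nearly excludes one of any size. The P<0.05 criterion treats them alike.

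**4. Effect of section 4.3 on an interval.** Assume 20 players per group, 4 of them imputed at the group mean, and an observed SD of 1.

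- Imputed data: SD = √(15/19) = 0.889; half-width = 2.024 × 0.889 × 0.316 = 0.57 SD.
- The 16 observed per group: half-width = 2.042 × √(2/16) = 0.72 SD.

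The imputed interval is 1 − 0.57/0.72 = 21% too narrow, although no information was added.

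**5. Pooled or unequal variances.** The plan does not say which form of the independent t-test applies. Simulation with assumed groups of 20 and 10 and an SD ratio of 1:1.5 gives:

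- smaller group has the larger SD: pooled type I error about 8.4% (up to 8.7% in repeat runs);
- larger group has the larger SD: pooled type I error about 2.7%;
- unequal-variance test: about 5% in both cases.

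With equal group sizes both tests stay at about 5%. With equal SDs at 20 vs 10, the unequal-variance test costs about 0.7 percentage points of power at 0.5 SD (up to 0.9 in repeat runs) and about 1.6 at 0.8 SD.

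**The case against.** The strongest reply is that the information is recoverable. The plan presents means and SDs, and a report would normally give group sizes, so a reader could compute the unadjusted difference and its interval. That stands, with limits. The plan does not commit to reporting group size. Mean imputation would make the rebuilt interval too narrow. A median and interquartile range do not yield the interval directly. The gap is therefore in what the plan commits to report, and a reader who infers that the study's aim cannot be answered at all goes further than the documents allow.

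A reader might also infer that the plan will report P≥0.05 as no effect. No section says so. The criterion only defines when a result is called significant, and the reference to inferential statistics in section 4 does not exclude intervals, although it does not promise them either.

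It is also fair to say that an interval alone does not separate a null result from an inconclusive one. That needs an important difference stated beforehand, which is why the fix requires one.

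Finally, nothing in the documents suggests unequal groups or unequal SDs. The variance choice is a minor safeguard.

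**Conclusion.** The point holds as a gap in the planned result and its interpretation, and it should be corrected. The supplied SAP names no between-group estimate, interval or important difference, and no sample size or power stands in their place. The planned between-group t-test is not invalid for this reason.

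The practical size depends on a group size that the documents do not give. Across 10 to 50 per group, the unreported 95% half-width runs from 0.94 to 0.40 SD. Across 15 to 50 per group, a true 0.5 SD benefit would miss P<0.05 in about 74% to 30% of trials. These figures assume equal groups, equal SDs, complete data and a two-sided 5% level. The unequal-variance figures apply only if group sizes and SDs both differ.

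**What to change.** In 4.1 and 4.2, keep the P value but add text along these lines:

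- The result for each outcome is the between-group mean difference (experimental minus control) with its two-sided 95% confidence interval. It is taken from the 'equal variances not assumed' row of the SPSS independent t-test, or from a baseline-adjusted model if one is used. The number analysed in each group is reported.
- The estimate and interval are calculated without the group-mean-imputed values of section 4.3.
- Before analysis, the investigators name and justify the smallest important difference for each primary outcome and say which sign means benefit.
- P≥0.05 is reported as inconclusive unless the interval excludes that difference.

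**Cost.** This takes a few sentences in the SAP and no new data, since SPSS already prints the difference, its interval and the unequal-variance row. The investigators must agree an important difference for the Tampa scale and the CAIT. Intervals will be wider without imputed values and conclusions may read less favourably. Leaving out imputed values removes the false precision but not any bias from players who miss assessments, so missing numbers should be shown by group. The power cost of the unequal-variance row is small, as shown in step 5 of the working.

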4.2 Secondary Outcomes

The primary analyses will compare experimental vs control group guidelines on their mean and standard deviation: (i) Y-balance test (ii) Pain anxiety symptom scale.

Comparison will be tested by using the Paired t test to find the significant difference within the intervention effects and between the two groups (Experimental control group and Experimental Group) using independent t-test. P values <0.05 has been considered statistically significant.

4.3 Missing Data

For players who do not attend the assessment, the mean imputation of the assessment scores from their allocation group has been used.

5. Informed Consent Forms (ICF)

Written consent will be gained from the amateur football players with Kinesio phobia along with chronic ankle instability using the consent forms attached to the application.

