3.5.2 Secondary outcomes

Y-balance test:

Absolute reach distance (cm) = (Reach 1 + Reach 2 + Reach 3) / 3. Relative (normalised) reach distance (%) = Absolute reach distance / limb length * 100 Composite reach distance (%) = Sum of the 3 reach directions / 3 times the limb length * 100.

Pain anxiety symptom scale:

Pain and anxiety symptom scale (PASS) is a 20-item self-report measure to assess painrelated anxiety. Each item is a 6-point scale anchored from 0 (never) to 5 (always). Total score is ranged from 0 (representing no pain anxiety) to 100 (representing severe pain anxiety.

4. Statistical Analysis Plan (SAP)

Descriptive and inferential statistics will be used. Normally distributed data will be presented by mean and standard deviation (SD), and non-normally distributed data will be presented by median and interquartile range. SPSS (version 24.0) will be used for all statistical analyses.

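### Filling missing scores with the player's own group mean (Section 4.3) makes the follow-up SD, standard error and p-value too small, so the 5% level does not hold when scores are missing

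*Combined protocol and SAP*

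**What the plan says.** Section 4.3 (Missing Data) contains one sentence on the subject: "For players who do not attend the assessment, the mean imputation of the assessment scores from their allocation group has been used". It is the only missing-data rule in the supplied text.

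Section 4.1, for the Tampa scale and the CAIT, uses a paired t-test within groups and a comparison "between the two groups (Experimental control group and Experimental Group) using independent t-test. P values <0.05 has been considered statistically significant". Section 4.2 repeats this wording for the Y-balance test and the Pain anxiety symptom scale. Neither section says whether the independent t-test is run on follow-up scores or on change from baseline.

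The SD is itself a reported and compared quantity. Section 4.1 says "The primary analyses will compare experimental vs control group guidelines on their mean and standard deviation", and the opening of Section 4 says "Normally distributed data will be presented by mean and standard deviation (SD"), with medians and interquartile ranges for non-normal data. Section 3.3 has all four scales measured at baseline.

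**The concern.** A value set equal to the mean of its own group carries no new information, but a standard t-test cannot tell it from a measured one. It leaves the group mean where it was, contributes zero to the sum of squared deviations, and raises both n and the degrees of freedom. The analysis then claims more precision than the data hold.

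The rule covers both primary and both secondary outcomes. In a between-group test on follow-up scores the error always runs one way, towards a smaller p-value, so a nominal 5% test gives more than 5% false positives and the reported SDs are understated. For paired or change-score tests the stated level is also unreliable, but the direction needs working out.

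**Working it through.** **Inputs.** From the documents: own-group mean imputation (Section 4.3); paired and independent t-tests with a 0.05 threshold (Sections 4.1 and 4.2). Assumed, because the supplied text does not give them: two-sided tests, 30 players per arm, equal SD in both arms, only follow-up scores missing, and missing completely at random (the case kindest to the rule). The number missing is varied.

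**1. Independent t-test on follow-up scores, same number missing in each arm.** Let n be the players per arm and m the number observed. The difference in means and the within-arm sums of squares are those of the observed players. Hence:

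- reported SD / correct SD = √[(m−1)/(n−1)]
- reported SE / correct SE: r = √[m(m−1) / (n(n−1))]
- true type I error = 2·P(T with 2m−2 df > r·t(0.975; 2n−2))

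With n = 30, t(0.975; 58) = 2.002. With nothing missing, r = 1 and the formula returns the plan's own 5.0%. For six missing (m = 24):

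- SD ratio = √(23/29) = 0.891
- r = √[(24×23)/(30×29)] = √(552/870) = 0.797
- the observed-data t statistic has only to exceed 0.797 × 2.002 = 1.594; on 46 df this has two-sided probability 0.118

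| Missing per arm (of 30) | SD ratio | SE ratio r | True type I error |
|---|---|---|---|
| 0 | 1.000 | 1.000 | 5.0% |
| 1 | 0.983 | 0.966 | 5.8% |
| 3 | 0.947 | 0.898 | 7.8% |
| 6 | 0.891 | 0.797 | 11.8% |
| 9 | 0.830 | 0.695 | 17.2% |

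The missing fraction drives the result and the sample size hardly matters: at 20% missing, the rate is 11.7% to 11.9% for 15, 20, 30, 50 or 100 per arm.

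**2. Same test, scores missing in one arm only.** With n₁ = n₂ = 30 and m₁, m₂ observed, r = √{[(m₁+m₂−2)/(n₁+n₂−2)] × (1/n₁+1/n₂)/(1/m₁+1/m₂)}, referred to m₁+m₂−2 df. With 1, 3, 6 and 9 missing the rate is 5.4%, 6.3%, 8.0% and 10.1%.

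**3. Paired t-test, or independent t-test on change, with baseline kept and follow-up imputed.** Let b and f be the baseline and follow-up SDs, ρ their correlation and q the observed fraction. In large samples:

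reported / true variance = q + (1−q)(b²−f²) / (f²/q + b² − 2ρbf)

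If f = b the second term vanishes. At q = 0.8 the SE ratio is then √0.8 = 0.89, which is too small. If f > b it is smaller still: 0.79 to 0.85 at f/b = 1.5 for ρ from 0.3 to 0.8. If f < b the second term is positive, and the SE ratio runs from 0.92 to 1.05 for f/b between 0.5 and 0.8. Null simulations with 30 per arm (40,000 trials per setting, bivariate normal scores, ρ 0.3 to 0.8, both tests) gave:

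| Missing per arm | f/b 0.5–0.8 | f/b = 1 | f/b = 1.5 |
|---|---|---|---|
| 1 | 4.7–5.3% | 5.1–5.5% | 5.5–5.9% |
| 6 | 4.0–7.1% | 7.5–7.9% | 9.3–11.7% |

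Repeat runs moved the ends of these ranges by a few tenths of a percentage point.

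**4. Observed scores only.** In the same simulations, t-tests restricted to observed scores gave 4.7% to 5.3% in every setting.

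**The case against.** The strongest case against this point is about its weight. The size rests on assumed sample size and drop-out. The 11.8% figure needs a fifth of players missing in both arms, and nothing in the supplied text suggests that level: players come from one institution, and the only duration stated is three weeks, for deep breathing. With one player missing in total the rate is 5.4%, and with none missing the rule does nothing. This stands as a limit on size. It does not rescue the rule, which should be valid whenever it is used.

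Second, the direction is certain only for follow-up scores. Sections 4.1 and 4.2 leave the choice open, and a change-score or paired test can even be slightly conservative if scores become clearly less variable. This also stands. Section 4.3 speaks of imputing assessment scores, so keeping baseline and filling in follow-up is the fair reading. If mean changes were imputed instead, the inflation would match that for follow-up scores, about 12% at 20% missing.

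Third, the SD is not understated everywhere: outcomes summarised by medians may show no SD. The statement is limited to follow-up SDs that are reported with scores missing.

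Fourth, analysing observed scores drops allocated players and is unbiased only if scores are missing completely at random. That is true, but if non-attendance relates to outcome, the group means after imputation carry exactly the same bias, because they are the observed means. The rule gains nothing on bias.

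Finally, that imputed values are counted as observed is an inference, but it is how values entered into a standard t-test behave, and no correction is stated.

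**Conclusion.** The point holds, and the rule should be changed. For an independent t-test on follow-up scores, the downward error in SD, standard error and p-value follows from algebra and occurs whenever any score is missing. Under the assumptions above, it is slight with one missing per arm and more than double the nominal rate with six. For paired or change-score tests, the 5% level is unreliable in a direction set by the ratio of follow-up to baseline SD, which the supplied text does not give.

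**What to change.** Delete the group-mean imputation from Section 4.3. State instead that each t-test uses players with observed scores (both visits for paired or change tests), in their allocated group, with n and degrees of freedom equal to the number observed, and that the number missing is reported per group. The same edit should say whether the independent t-test uses follow-up or change scores.

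Two alternatives are acceptable, and both use the baseline scores already collected under Section 3.3: a between-group model adjusted for baseline, or multiple imputation that includes group and baseline, combined by Rubin's rules.

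The cost is about one sentence in the SAP, and SPSS can do every option. Section 4.3 is written in the past tense, so any analysis already run under the rule should be repeated. The downside is that p-values and intervals will generally be somewhat less favourable when scores are missing. The observed-scores option restores about 5% if scores are missing completely at random.
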